6.10. Continuous Glucose Monitoring Analysis	20
6.10.1. General Considerations	20
6.10.2. CGM Variable and Analysis.....	20
6.10.2.1. Target Glucose Range.....	20
6.10.2.2. Hypoglycemia	21
6.10.2.3. Hyperglycemia	21

6.10.2.4. Glycemic Variability	21
6.10.2.5. Mean glucose	21
6.10.2.6. iAUC and mean postprandial sensor glucose excursions	21
6.10.2.7. Highest sensor glucose	21
6.10.2.8. Target CGM glucose	22
6.10.2.9. Other CGM variables.....	22
6.11. Subgroup Analyses.....	22
6.12. Interim Analyses	23
6.13. Data Monitoring Committee (DMC)	23
7. References	24
8. Appendices	25

Table of Contents

Table		Page
Table ITSW.4.1. Objectives and Endpoints		8
Table ITSW.6.1. Baseline and Post-Baseline Definitions and Patient Population by Type of Analysis.....		14

Table of Contents

Figure		Page
Figure ITSW.5.1.Illustration of study design.....		12

Table of Contents

Appendix		Page
Appendix 1.	Derivation of CGM Variables	26

3. Revision History

This statistical analysis plan (SAP) is the first version and is based on the protocol of I8B-MC-ITSW approved on 21 April 2020 and the following amendments (a) approved on 13 July 2020. This SAP was approved prior to the first patient visit.

4. Study Objectives

Table ITSW.4.1. Objectives and Endpoints

Objectives	Endpoints
Primary	

 To evaluate time glucose values from continuous glucose monitoring (CGM) are within target range (70-180 mg/dL [3.9-10.0 mmol/L]) during the daytime period with LY900014 treatment 	
 Percentage of time with CGM glucose values between 70-180 mg/dL (3.9-10.0 mmol/L) (both inclusive) during daytime period with 14 days of CGM use at Week 12 compared with baseline
Gated Secondary	

 To evaluate HbA1c 	
 HbA1c change from baseline to Week 12

 To evaluate time glucose values from CGM are within target range (70-180 mg/dL [3.9-10.0 mmol/L]) during the 24-hour period with LY900014 treatment 	
 Percentage of time with CGM glucose values between 70-180 mg/dL (3.9-10.0 mmol/L) (both inclusive) during the 24-hour period with 14 days of CGM use at Week 12 compared with baseline
Other Secondary	

 To evaluate time in hypoglycemic glucose ranges, obtained from CGM use 	
 Percentage of time with CGM glucose values <54 mg/dL (<3.0 mmol/L) during daytime and 24-hour periods with 14 days of CGM use at Week 12 compared with baseline

 To evaluate time in hyperglycemic glucose ranges, obtained from CGM use 	
 Percentage of time with sensor glucose values >180 mg/dL (>10.0 mmol/L) and >250 mg/dL (>13.9 mmol/L), during daytime and 24-hour periods with 14 days of CGM use at Week 12 compared with baseline

 To evaluate postprandial incremental AUCs, obtained from CGM use 	
 Postprandial incremental $AUC_{0-1\text{ hour}}$ and incremental $AUC_{0-2\text{ hour}}$ at Week 12 compared with baseline

 To evaluate proportion of participants achieving HbA1c targets 	
 The proportion of participants with $HbA1c < 7\%$ and $\leq 6.5\%$ at Week 12

 To evaluate bolus, basal, and total daily insulin dose 	
 Bolus, basal, and total insulin doses and bolus/total insulin ratio at Week 12 compared with baseline

 To evaluate severe hypoglycemia 	
 Incidence of severe hypoglycemia events from baseline to Week 12

 To evaluate insulin treatment satisfaction regarding glycemic control as measured by the ITSQ 	
 Change from baseline in ITSQ glycemic control domain scores at Week 12
Tertiary/Exploratory	

 To evaluate proportion of participants achieving CGM-based glycemic targets 	
 The proportion of participants with percentage of time in target CGM glucose range ($70-180\text{ mg/dL}$ [$3.9-10.0\text{ mmol/L}$]) $>70\%$, time in hypoglycemia ($<54\text{ mg/dL}$ [$<3.0\text{ mmol/L}$]) $<1\%$, and time in hyperglycemia ($>250\text{ mg/dL}$ [$>13.9\text{ mmol/L}$]) $<5\%$ with 14 days of CGM use at Week 12

 To evaluate glucose profiles, obtained from CGM use 	
 Average glucose for a 24-hour period from each 14-day CGM session at Week 12 compared with baseline

 To evaluate glucose variability, obtained from CGM use 	
 CV with 14 days of CGM use at Week 12 compared with baseline

 To evaluate insulin treatment satisfaction as measured by the ITSQ 	
 Change from baseline in ITSQ total and domain scores (except glycemic control domain) at Week 12

• To characterize participants' willingness to incorporate LY900014 into diabetes management routine	
• Distribution of responses to study mealtime insulin experience question at Week 12

• To evaluate attitudes towards diabetes technology use as measured by the DSAT	
• Change from baseline in DSAT total score at Week 12

5. Study Design

5.1. Overall Design

Study ITSW is a Phase 3b, prospective, open-label, outpatient, multicenter, single-treatment-group study conducted in participants with type 2 diabetes (T2D) currently treated with a basal-bolus analog multiple dose injection (MDI) regimen. Participants will use unblinded continuous glucose monitoring (CGM) (Freestyle Libre 14-day system) for diabetes management and glucose data collection during the study. The study is designed to evaluate the time sensor glucose values from CGM are within target range (70-180 mg/dL [3.9-10.0 mmol/L]) with 12 weeks of LY900014 treatment.

LY900014 will be injected immediately (0-2 minutes) prior to each meal in combination with insulin glargine U-100 (Basaglar®) as basal insulin. Basal-bolus insulin doses will be titrated to achieve protocol glucose targets during the study.

5.2. Sample Size Determination

Approximately 167 participants will be assigned to treatment with LY900014 such that 150 participants complete the study through the primary endpoint at Week 12.

The primary objective of this study is to evaluate the change of time glucose values from CGM are within target range (70-180 mg/dL [3.9-10.0 mmol/L]) during the daytime period from baseline to endpoint at Week 12 with LY900014 treatment.

This sample size has approximately 80% power to detect an increase of 4.5% time in target range (70-180 mg/dL [3.9-10.0 mmol/L]) during the daytime period from baseline, assuming no true difference in time in target range between baseline and endpoint, and a standard deviation (SD) of 19.5%. Assuming a 10% dropout rate for 12 weeks, approximately 167 participants will need to be assigned.

[figure not shown]

Figure ITSW.5.1. Illustration of study design.

6. A Priori Statistical Methods

6.1. Populations for Analyses

The following populations are defined:

Population	Description
Entered	All participants who give informed consent
Enrolled	All participants who continue the study after Visit 2.
Treated	All enrolled participants who receive at least 1 dose of the assigned IP after Visit 4

Abbreviations: IP = investigational product.

6.2. General Considerations

Statistical analysis of this study will be the responsibility of Lilly or its designee. Any change to the data analysis methods described in the protocol will require an amendment ONLY if it changes a principal feature of the protocol. Any other change to the data analysis methods described in the protocol, and the justification for making the change, will be described in the statistical analysis plan (SAP) or the clinical study report (CSR). Additional exploratory analyses of data will be conducted as deemed appropriate.

Efficacy analyses will be conducted on the treated population, including data collected prior to permanent discontinuation of IP. When change from baseline is included as a *response variable of analysis models*, the participant will be included in the analysis only if a baseline and a postbaseline measurement are available.

Safety analyses will be conducted on the treated population. Analyses of adverse events (AEs) and severe hypoglycemia will include data collected during the treatment period and baseline period. Adverse events during the follow-up period will be listed.

Unless otherwise noted, all tests will be conducted at a 2-sided alpha level of 0.05, and confidence intervals (Cis) will be calculated at 95%, 2-sided. A gatekeeper method (Westfall and Krishen 2001) will be used to control the overall type 1 error for the primary and gated secondary objectives.

Baseline is defined as the last nonmissing measurement at or before Visit 4 unless otherwise specified.

A restricted-maximum-likelihood-based, mixed model repeated measures (MMRM) analysis will be used to analyze continuous longitudinal variables. All the longitudinal observations at each scheduled postbaseline visit will be included in the analysis. The model for the analysis of the primary efficacy endpoint of change from baseline in time in target range (70-180 mg/dL [3.9-10.0 mmol/L]) during daytime period will include the fixed class effect of visit, the covariate of baseline, and the random effect of participant. An unstructured covariance structure will be used to model the within-participant errors. Significance tests will be based on least-squares means and Type III tests. SAS® PROC MIXED will be used to perform the

analysis. If this analysis fails to converge, the following covariance structures will be tested in order:

- Toeplitz with heterogeneity
- autoregressive with heterogeneity
- compound symmetry with heterogeneous variances
- Toeplitz
- autoregressive
- compound symmetry without heterogeneous variances

The first covariance structure that converges will be used. The Kenward-Roger approximation will be used to estimate denominator degrees of freedom.

An analysis of covariance (ANCOVA) will also be used to analyze continuous variables collected only at baseline and endpoint. The model will include baseline as a covariate. Unless otherwise stated, missing endpoints will be imputed using the last-observation-carried-forward (LOCF) approach, using only postbaseline data.

For continuous measures, summary statistics will include sample size, mean, standard deviation (SD), median, minimum, and maximum for both the actual and the change from baseline measurements. Least-square means and standard errors derived from the analysis models will also be displayed for the change from baseline measurements.

For categorical measures, summary statistics will include sample size, frequency, and percentages.

Table ITSW.6.1. Baseline and Post-Baseline Definitions and Patient Population by Type of Analysis

Analysis	Patient Population	Baseline Observations	Post-Baseline Observations
HbA1c MMRM	All treated patients with a baseline and at least one post-baseline observation	Last of Visits 1-4	Visits 7, 9, and 12 prior to discontinuation of IP
HbA1c categorical analysis longitudinal logistic regression	All treated patients with a baseline and at least one post-baseline observation	Last of Visits 1-4	Visits 7, 9, and 12 prior to discontinuation of IP
CGM outcomes	All treated patients with a baseline and at least one post-baseline observation	Visit 4	Visits 7, 9, and 12 prior to discontinuation of IP
Basal, bolus, and total insulin doses, and bolus/total insulin dose	All treated patients with a baseline and at least one	Visit 4	Visits 6, 7, 9, and 12 prior to discontinuation of IP

ratios continuous analysis	post-baseline observation		
Health outcomes: ITSQ, DSAT	All treated patients with a baseline and a post-baseline observation	Last of Visits 2-4	Visit 12 prior to discontinuation of IP
Health outcome: Study mealtime insulin experience question	All treated patients with a post-baseline observation	NA	Visit 12 prior to discontinuation of IP
Weight and vital signs	All treated patients with a baseline and at least one post-baseline observation	Last of Visits 1-4	Visits 7, 9, and 12 prior to discontinuation of IP
Severe Hypoglycemia events	All treated patients	The entire baseline period	The entire treatment period
TEAEs	All treated patients	From Visit 2 to the first dose of assigned IP	From first dose of assigned IP to last dose of assigned IP Follow up period
Postprandial incremental AUCs	All treated patients with a baseline and a post-baseline observation	Visit 4	Visit 12 prior to discontinuation of IP

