6.8.2. Gated/Other Secondary Endpoints

The analysis of the secondary gated objectives will be conducted if the time in target range (70-180 mg/dL [3.9-10.0 mmol/L]) during the daytime period at study endpoint versus baseline is found statistically significant for the primary efficacy analysis at a 2-sided 0.05 significance level (Westfall and Krishen 2001). If this contrast is significant, the secondary objectives were tested in sequence until the first null hypothesis in the sequence failed to be rejected at a 2-sided 0.05 significance level. The sequential testing for gated secondary objectives is conducted in the following order to assess whether value at study endpoint is superior to baseline:

1. To evaluate HbA1c
2. To evaluate time glucose values from CGM are within target range (70-180 mg/dL [3.9-10.0 mmol/L]) during the 24-hour period.

For continuous longitudinal secondary endpoints, the MMRM model similar to that for the primary analysis will be used. Duration and percent time in range, time in hypoglycemia, and time in hyperglycemia derived from CGM data will also be analyzed using an MMRM model. Details for the CGM analyses can be found in Section [6.10](#).

Continuous nonlongitudinal secondary endpoints will be analyzed using the ANCOVA. Postprandial incremental area under the curve (AUC)₀₋₁ hour and incremental AUC₀₋₂ hour will be analyzed by ANCOVA described in Section [6.2](#).

Proportion of participants with HbA1c <7.0% and \leq 6.5% will be analyzed using a longitudinal logistic regression with repeated measurements conducted by a generalized linear mixed model with the fixed class effect of visit, the covariate of baseline HbA1c, and the random effect of participant.

Actual and change from baseline in basal, bolus, and total dose, as well as the bolus/total insulin dose ratio will be analyzed by the MMRM models described in Section [6.2](#).

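### The primary single-arm test of change from baseline uses a standard error that omits the sampling variance of the baseline mean, so for the population mean change it rejects too often

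*SAP*

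**What the plan says.** - **Design and objective.** Protocol 6.3 describes an open-label, single-arm study. SAP 5.2 states: "The primary objective of this study is to evaluate the change of time glucose values from CGM are within target range", measured in the daytime from baseline to Week 12.
- **Primary model.** SAP 6.2 and Protocol 9.4.1 analyse change from baseline with a model that "will include the fixed class effect of visit, the covariate of baseline, and the random effect of participant", with an unstructured covariance, PROC MIXED and Kenward-Roger degrees of freedom.
- **Basis of the test.** SAP 6.2: "Significance tests will be based on least-squares means and Type III tests".
- **Gate.** SAP 6.8.2 opens the gated tests only if the primary contrast of endpoint with baseline is significant at two-sided 0.05. It then tests HbA1c and 24-hour time in range in order, "to assess whether value at study endpoint is superior to baseline".
- **Reach of the model.** SAP 6.8.2: "For continuous longitudinal secondary endpoints, the MMRM model similar to that for the primary analysis will be used". For the ANCOVA variables, SAP 6.2 says: "The model will include baseline as a covariate".

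Neither document says at which baseline value the least-squares mean is evaluated, asks for a robust standard error, places baseline among the responses, or limits inference to the baselines actually observed.

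**The concern.** Adjusting for baseline is routine when two arms are compared: both least-squares means are evaluated at the same baseline value, so uncertainty about that value drops out of the difference. Here the least-squares mean itself is tested against zero. If change depends on baseline, as regression to the mean alone would cause, a different sample would have a different baseline mean and hence a different mean change. The model's standard error ignores that variation. Kenward-Roger does not restore it, because it corrects for estimated covariance parameters and not for a random covariate mean. The Type III test of visit does not help either, because it compares post-baseline visits with one another.

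At stake is the error control that SAP 6.2 claims for the primary and gated objectives. The primary test opens the gate, and both gated tests use the same model form.

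**Working it through.** **Inputs.** From SAP 5.2 and 6.2: two-sided alpha 0.05, increase 4.5 points, SD 19.5, 150 completers, 10% dropout, 167 assigned. Assumed, because the documents do not give them: the correlation ρ between baseline and Week 12, and the ratio k of Week 12 SD to baseline SD.

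**The plan's own figure.** A one-sample test of mean change needs ((1.960 + 0.842) × 19.5/4.5)² = 147.4 participants by the normal formula. The noncentral t gives 150, with power 80.2%; 150/0.9 = 166.7, so 167. The stated size is therefore reproduced by a plain paired test with 19.5 as the SD of change. The documents do not say which SD 19.5 is.

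**The missing variance.** Set the baseline SD to 1 and the Week 12 SD to k.

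- Slope of change on baseline: b = ρk − 1
- Variance of change: V = 1 + k² − 2ρk
- Share of V explained by baseline: R² = b²/V
- True sampling variance of the mean change: V/n
- Variance the model reports: V(1 − R²)/n
- Size of the nominal 5% test: 2 × (1 − Φ(1.96 × √(1 − R²)))

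Example with k = 1 and ρ = 0.5: b = −0.5, V = 1, R² = 0.25, √(1 − R²) = 0.866, and size = 2 × (1 − Φ(1.697)) = 9.0%.

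| Analytic size | ρ = 0.3 | 0.5 | 0.7 | 0.8 |
|---|---|---|---|---|
| k = 0.8 | 16.5% | 13.8% | 12.0% | 11.7% |
| k = 1.0 | 11.4% | 9.0% | 7.1% | 6.3% |
| k = 1.2 | 8.7% | 6.7% | 5.4% | 5.0% |

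The inflation vanishes when ρk = 1, that is, when change and baseline are uncorrelated.

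**Check by simulation.** These runs used n = 150, baseline plus three visits, an unstructured REML model with a common baseline slope, and 20,000 null trials per cell. Columns are ρ = 0.3/0.5/0.7/0.8, where ρ is always the baseline-to-Week 12 value.

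| k | Constant correlation | Correlation decaying with time |
|---|---|---|
| 0.8 | 16.8/13.9/12.3/11.6% | 14.8/12.3/11.5/10.9% |
| 1.0 | 11.4/8.7/6.9/6.2% | 10.1/8.1/6.8/5.8% |
| 1.2 | 8.4/6.8/5.5/4.8% | 7.9/5.7/4.6/4.8% |

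The paired test gave 4.7% to 5.4% in every cell. A separate simulation with 167 assigned, 10% dropout and equal SDs gave 11.5%, 9.2% and 6.6% at ρ = 0.3, 0.5 and 0.8. At ρ = 0.3 its mean model standard error was 1.48, against an actual standard deviation of the estimate of 1.82.

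**In time-in-range points.** If 19.5 is the SD of change and n = 150, the paired test needs an observed mean change of 1.976 × 19.5/√150 = 3.15 points. Multiplying by √(1 − R²), the planned model with equal SDs needs only 2.54, 2.72, 2.90 or 2.98 points at ρ = 0.3, 0.5, 0.7 or 0.8.

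**The case against.** **The test is valid conditional on the observed baselines.** This is true, and conditioning on covariates is ordinary regression practice. But the objective and the gate are worded as endpoint against baseline with no such condition, and the sample size matches the unconditional paired test. The population reading is an inference from the documents, though the natural one.

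**The size rests on assumed correlations and SDs.** This stands. With correlations that decay over time the equal-SD range is 5.8% to 10.1%, and at k = 1.2 with ρ of 0.7 or more the test is close to nominal. The mechanism is certain; its size in this trial is not.

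**The practical effect is small.** Largely true. An observed 4.5-point change gives z = 4.5/(19.5/√150) = 2.83 (p = 0.005) on the paired test, if 19.5 is the SD of change. With equal SDs and a true effect of 4.5 points, the two tests disagree in only about 3% to 9% of trials. In an open-label study with titration and unblinded monitoring, the p-value does not isolate a drug effect anyway. The interval is nevertheless too narrow whatever the p-value.

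**The planned tables expose the gap.** The n and SD of change are to be tabulated, so a reader could form the paired standard error. That does not correct the gate.

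**The covariance fallbacks could spoil the repair.** With baseline among the responses, a compound-symmetry fallback under decaying correlation and equal SDs gives a size of 11.0%, 12.3% and 13.7% at ρ = 0.3, 0.5 and 0.8. This matters only if the earlier structures, starting with a 4 × 4 unstructured matrix on about 150 participants, fail to converge. The replacement text should still cover it.

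**Conclusion.** The concern holds. For the population mean change, the primary test is anti-conservative and its interval too narrow whenever change is correlated with baseline. With equal SDs the size is about 6% to 11% for ρ from 0.8 to 0.3; across k = 0.8 to 1.2 it runs analytically from 5.0% to 16.5%. Both ranges rest on assumed ρ and k. HbA1c, 24-hour time in range and the ANCOVA endpoints share the defect, but its size there was not quantified. It should be corrected because the plan claims type 1 error control, although only borderline results would change.

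**What to change.** Replace the model sentence in SAP 6.2 and Protocol 9.4.1 with:

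> Observed values at baseline and at Visits 7, 9 and 12 will be modelled as repeated responses, with visit as fixed class effect and an unstructured within-participant covariance; the test is the Visit 12 minus baseline contrast.

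- **Scope.** Use this for daytime time in range, HbA1c and 24-hour time in range. Keep the analysis set and baselines of Table ITSW.6.1: Visit 4 for CGM outcomes, and for HbA1c "Last of Visits 1-4". For variables measured only at baseline and endpoint, use the unadjusted paired mean change.
- **Performance.** With complete data the contrast equals the paired test. With 167 participants, about 10% missing-at-random dropout and decaying correlation, its size was 4.3% to 5.3% (4,000 trials per cell).
- **What to avoid.** Do not keep the current model and add slope² × Var(baseline)/n to its variance. With a common slope and decaying correlations, that gave sizes up to 7.6%.
- **Fallback.** State what will be done if the unstructured fit fails, and do not carry over the present list unexamined.
- **Wording only.** Drop the random participant effect, which is redundant with an unstructured covariance.

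**Cost.** Text changes in two documents and no new data. SAP 6.2 says a change to the protocol's analysis methods "will require an amendment ONLY if it changes a principal feature of the protocol"; the sponsor must decide whether the primary model is one. Intervals widen by the factor 1/√(1 − R²): 5% to 24% with equal SDs (ρ from 0.8 to 0.3), 25% to 41% at k = 0.8, and 0% to 15% at k = 1.2.

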6.3. Patient Disposition

Patient disposition will be displayed in a flowchart showing the number of patients entered, enrolled, treated, and discontinued across all study periods.

Frequency counts and percentages of all treated patients completing and discontinuing from the study will be presented. Reasons for discontinuation from the study and study treatment will be summarized.

Frequency counts and percentages of all patients entered, enrolled, and discontinued from the study during the baseline period will be summarized. Reasons for discontinuation during screening will be summarized for all entered patients. Reasons for discontinuation during the baseline period will be summarized for all enrolled patients.

A listing of the primary reason for treatment discontinuation (if applicable) and study discontinuation will be generated for the treated population.

Patient allocation by investigator will be summarized indicating the number of patients who enter the study, the number of patients who participate in the baseline period, the number of

patients treated, and the number of patients who discontinue the study during the 12-Week treatment period.

